Trauma Informed Guilt Reduction Therapy

NCT02512445

Original Document Date: November 14, 2024

8. Aims and Objectives

Primary Aim: To evaluate the efficacy of TrIGR for reducing deployment-related guilt in Veterans of OEF/OIF/OND.

Hypothesis 1: Veterans in TrIGR compared to Veterans in supportive care therapy (SCT), will have significantly greater reductions in deployment-related guilt severity at the end of treatment and post-treatment follow-up.

Secondary Aims: To examine whether TrIGR reduces distress and shame and improves quality of life. We are also interested in the degree to which gains are maintained during the follow up periods.

Hypothesis 2: Veterans in TrIGR, compared to Veterans in SCT, will have significantly greater reductions in distress, shame, guilt cognitions, avoidant coping, and significantly more improvement in their quality of life at the end of treatment and at post-treatment follow-up.

Hypothesis 3: Per the NAG model, guilt cognitions, distress and avoidant coping will partially mediate the treatment effect on guilt severity.

Exploratory Aim: By including Veterans with a variety of deployment-related presenting problems, we will be able to conduct exploratory analyses that will inform future research regarding for whom and under what conditions TrIGR is most effective.

Objective 1: To explore relationships between TrIGR effects and PTSD and depression symptom severity, suicidal ideation (SI) and alcohol/substance use.

Objective 2: To explore whether reductions in guilt, shame, and avoidant coping will partially mediate the treatment effect on PTSD symptoms among **Veterans with a PTSD diagnosis** and/or depression symptoms among **Veterans with a depressive disorder**.

9. Approach

9.1. Design. This prospective, randomized, controlled trial will assess the efficacy of TrIGR as compared to SCT for the treatment of male and female Veterans with guilt related to a traumatic event that occurred during deployment. 150 participants will be enrolled through the San Diego and Providence VAs and randomized at the individual level. All eligible participants will complete an in-person baseline assessment, receive 6 sessions of TrIGR or SCT in individual format, complete weekly measures related to the primary and secondary aims, and complete a follow-up assessment immediately post-treatment, and 3- and 6-months later.

9.2. Timeline. We propose a study lasting 4 years including:

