9.8. Research Assessments

9.8.1. Outcomes. The primary efficacy outcomes of interest are reduction in the severity of guilt related to a deployment trauma at post-treatment and follow-up. We will also examine distress, shame,

quality of life, PTSD symptoms, depression symptoms, alcohol and substance use, suicidality, and potential mediators and moderators including avoidant coping, guilt cognitions, treatment process variables (e.g., attendance, homework completion), gender, and cognitive performance. All measures can be found under Support Documents.

Primary Outcome. Trauma Related Guilt Inventory [TRGI; 18] is a 32-item validated self-report measure assessing traumatic guilt. The TRGI has three scales – Guilt Severity, Distress, and Guilt Cognitions. We will use the TRGI as one of our eligibility criteria (see inclusion criteria, section 9.4) and to monitor changes in guilt and related cognitions over time. Guilt severity will be the primary outcome of interest. It is computed by adding items regarding guilt frequency and guilt intensity. Changes in guilt cognitions will be examined as a partial mediator of treatment outcomes. Internal consistency is high for the TRGI (guilt severity = .90, distress = .86, guilt cognitions = .86).

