Secondary Outcomes. The Brief Symptom Inventory-18 [BSI-18; 50] will be used for inclusion criteria and to assess change in self-reported distress over the study period. The 18 items are on a five-point Likert scale assessing the degree to which participants were distressed or bothered by mental health problems in the last seven days. The BSI-18 generates four scores: a total score [global severity index (GSI); scores ranging from 0 to 72], and three subscale scores for depression, somatization, and anxiety (scores ranging from 0 to 24). Internal consistency for the BSI is adequate ($\alpha = .89$ for GSI, $\alpha = .84$ for depression, $\alpha = .74$ for somatization, and $\alpha = .79$ for anxiety) and concurrent validity with the longer-form measure the BSI-18 was derived from ranges from .91 to .96. A Clinical Global Impressions Severity Scale [CGI-S; 51] rating of at least markedly ill will be required for study entry. The CGI-S requires clinicians to make two ratings on a 7-point categorical scale: (1) severity of illness within last seven days, and (2) global improvement from baseline. The CGI-S is commonly used in clinical trials to assess changes in distress severity, and has shown predictive utility in studies of schizophrenia, depression, social anxiety, and PTSD. We will use the CGI-S to assess clinician ratings of change in distress severity. In combination, the BSI-18 and the CGI-S will allow us to have multi-modal assessment (i.e. self-report and clinician rating) of distress severity.

We will measure shame using the Internalized Shame Scale [ISS; 66], a 30-item self-report measure assessing shame proneness scored on a 5-point Likert scale. The ISS yields sum scores for two subscales, self-esteem and internalized shame and has been well-validated with research and clinical populations. The World Health Organization Quality of Life [WHO-QOL-BREF; 89] is a 26-item measure that assesses quality of life across four domains: physical, psychological, social relationships, and environment. The WHO-QOL-BREF has excellent internal validity and test-retest reliability.

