In the second stage, we will perform sensitivity analyses for the impact that potentially informative missing data may have on the analyses. The selected method of data analysis is robust with respect to drop-out and missing data, unless the drop-out mechanism or cause of missing is informative. We will use pattern-mixture models to assess if there is bias due to drop out or missing data. These mixed models allow us to assess whether important estimates are dependent on missing data patterns, and provide overall estimates of effects by averaging over the various missing-data patterns [80]. In addition, we will consider the extension of the Pattern-Mixture models [81], which includes the incorporation of random effects in the Pattern mixture model, which allow subject-to-subject heterogeneity. All hypothesis tests will be intent-to-treat, using SPSS version 21, and will be two-sided at the .05 level where applicable. We will adjust p-values for multiple testing within each hypothesis separately by using a Bonferroni correction whenever more than one variable is being tested.

Type I error will be controlled through the following steps. The data analysis method we selected reduces the number of dependent variables drastically. We have restricted potential predictors to those with strong evidence and/or strong rationale for having an effect on the dependent variable, and in most cases we have further restricted potential predictors to one representative of each. Also, an adjusted significance level (.01 rather than .05) will be used if applicable.

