Data will be analyzed from all randomized subjects on whom we have a baseline assessment and at least one post-baseline evaluation. Responses at baseline through 6 months follow-up will be nested within subjects. Slope (change in outcome over time) will be entered into the model as a random factor and interacted with treatment group. Intercept and slope will be modeled as random effects nested within subject, and treatment group will be a fixed effect. If it is needed based on analyses in stage one, baseline covariates (e.g., demographics) will also be entered as fixed effects. Site and the Treatment by Site interaction will be included as “nuisance parameters;” that is, they must be included to account for possible overall site effects (Site) or possible site differences in treatment effects (Treatments X Site). With the balanced design (equal numbers at each site in each group), ignoring these would not increase the probability of Type I error, but it would increase the Error Sum of Squares, thus increasing the probability of Type II Error. The main effect of treatment represents the common effect size across sites if there is one, or the average site effect, if there is heterogeneity across sites. This is true because sample sizes will be balanced across treatment groups and sites. In any case, the analysis procedures will include site and site interaction effects to avoid allowing site effects to bias treatment comparisons. However, if we detect any imbalances between the treatment groups within each site, we will follow the primary analyses above with subsequent analyses considering the imbalances to verify that the conclusions are not affected by the imbalances.

Hypothesis 2: Veterans in TrIGR, compared to Veterans in SCT, will have significantly greater reduction in distress (BSI-18), shame (ISS), and significantly more improved in their quality of life (WHO-QOL-BREF) at the end of treatment and at follow up periods. This hypothesis will be analyzed using a method similar to that for testing hypothesis 1.

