Hypothesis 3: Per the NAG model, guilt cognitions (TRGI Cognitions Scale), distress (BSI-18) and avoidant coping (COPE) will partially mediate the treatment effect on guilt severity (TRGI). For this hypothesis, we will use the same mixed effect model procedure identified in hypothesis 1. We will utilize the analytic strategy described by [85] [86] to test the mediation effect. Based on this strategy, four conditions must be met: (1) a significant relationship between the independent variable (i.e., intervention

condition) and the dependent variable, (2) a significant relationship between the independent variable and the proposed mediator, (3) a significant relationship between the mediator and the outcome, and (4) the relationship between the independent variable (intervention) and outcome must be significantly lower after controlling for the proposed mediator. To test for significant mediation, we will conduct a Sobel test. We will also use the formula provided by [87] to determine the percentage of the intervention condition to primary outcome path that was accounted for by change in our mediator [88].

Exploratory Analyses. The first exploratory objective, whether TrIGR, as compared to SCT, is associated with greater decreases in PTSD and depression symptom severity, greater reductions in suicidal ideation (SI) and greater reductions in alcohol/substance use, will be explored using mixed effect method as explained for hypothesis 1. The second and third objectives—whether reductions in guilt, shame, and avoidant coping will partially mediate the treatment effect on PTSD symptoms among Veterans with a PTSD diagnosis and among Veterans with a depressive disorder—will be explore using analytic strategy as described for hypothesis 3 [85].

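### Hypothesis 2 has five outcomes in section 8 but three in section 9.11.2, so the divisor for its within-hypothesis Bonferroni correction is not fixed

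*Combined protocol and SAP*

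**What the plan says.** - **Section 8, Hypothesis 2** (five outcomes): TrIGR participants "will have significantly greater reductions in distress, shame, guilt cognitions, avoidant coping, and significantly more improvement in their quality of life".
- **Section 8, Secondary Aims** (three constructs): "To examine whether TrIGR reduces distress and shame and improves quality of life".
- **Section 9.11.2, Hypothesis 2** (three outcomes, instruments named): "will have significantly greater reduction in distress (BSI-18), shame (ISS), and significantly more improved in their quality of life (WHO-QOL-BREF".
- **Section 9.8.1, opening paragraph**: the other two constructs are among the "potential mediators and moderators including avoidant coping, guilt cognitions".
- **Section 9.11.2, Hypothesis 3**: "guilt cognitions (TRGI Cognitions Scale), distress (BSI-18) and avoidant coping (COPE) will partially mediate the treatment effect on guilt severity (TRGI".
- **Section 9.11.1, multiplicity**: "We will adjust p-values for multiple testing within each hypothesis separately by using a Bonferroni correction whenever more than one variable is being tested". The next paragraph adds that "an adjusted significance level (.01 rather than .05) will be used if applicable", with no trigger, no named hypothesis and no stated relation to Bonferroni.
- **Section 9.8.1, Secondary Outcomes**: the BSI-18 and the clinician-rated CGI-S both measure change in distress, the ISS yields two subscale scores, and the WHO-QOL-BREF "assesses quality of life across four domains: physical, psychological, social relationships, and environment". Apart from naming the instruments, section 9.11.2 does not say which score is tested.

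**The concern.** Both statements of Hypothesis 2 are operative text, and they disagree on what belongs to the hypothesis. Because the correction is defined per hypothesis, the length of the list is the divisor. Two things follow.

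- A raw p-value between 0.0100 and 0.0167 is significant under one section and not under the other.
- It is unclear whether effects on guilt cognitions and avoidant coping may be reported as confirmatory Hypothesis 2 results or only as steps in the mediation analysis.

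If this stays open, both choices could be made once the p-values are known.

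**Working it through.** **1. Inputs.** Two-sided family level 0.05 and within-hypothesis Bonferroni (section 9.11.1). Five outcomes (section 8) or three (section 9.11.2). From the power analysis: 150 participants, a difference rising linearly from 0 to 0.5 SD at the last visit, 10% to 20% attrition, and correlations of 0.2, 0.5 and 0.8. Allocation is equal (section 9.5.2), so 75 per arm. There are four assessments (section 9.3).

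**2. The plan's own figure.** The plan prints no Bonferroni level and no test count. Its only number for Hypothesis 2 is 80% power (90% for Hypothesis 1), without the alpha or a single correlation, so it cannot be reproduced uniquely. I used a generalised least squares test of treatment by linear time, normal approximation: power = Φ(0.5/SE − z at 1 − α/2). Assumed, not in the documents: compound symmetry, visits at 0, 1.5, 4.5 and 7.5 months, and dropout spread evenly over the three post-baseline visits. With correlation 0.5 and 10% attrition, power is 89.2% at 0.05, 78.8% at 0.0167 and 73.2% at 0.0100. The stated 90% and 80% are thus approached with Hypothesis 2 at 0.05/3, but this is only suggestive, since other stated correlations give very different values.

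**3. Levels, one score per construct.**
- Three tests: 0.05/3 = 0.0167.
- Five tests: 0.05/5 = 0.0100.

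**4. Levels if more scores are tested.**

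| Added to the list | From three | From five |
|---|---|---|
| CGI-S as well as BSI-18 (+1) | 0.05/4 = 0.0125 | 0.05/6 = 0.0083 |
| Two ISS subscales instead of one score (+1) | 0.05/4 = 0.0125 | 0.05/6 = 0.0083 |
| Four WHO-QOL-BREF domains instead of one score (+3) | 0.05/6 = 0.0083 | 0.05/8 = 0.0063 |
| All of these (+5) | 0.05/8 = 0.0063 | 0.05/10 = 0.0050 |

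**5. Family-wise error if all five are claimed at the three-test level.** Bound: 5 × 0.05/3 = 0.0833. If the tests were independent: 1 − (1 − 0.05/3)^5 = 0.0806. Both exceed 0.05.

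**6. Chance that one outcome's p-value falls between the levels.** The critical values are 2.394 (0.0167) and 2.576 (0.0100). With correlation 0.5 and 20% attrition, SE = 0.1637 and the expected z is 0.5/0.1637 = 3.05. Power is Φ(3.05 − 2.394) = 0.746 at 0.0167 and Φ(3.05 − 2.576) = 0.684 at 0.0100, a difference of 0.062. Over the plan's ranges:

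| Attrition | Correlation 0.2 | 0.5 | 0.8 |
|---|---|---|---|
| 10% | 0.072 | 0.056 | 0.003 |
| 20% | 0.072 | 0.062 | 0.005 |

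For a normal test statistic no effect size gives more than 2Φ((2.576 − 2.394)/2) − 1, about 0.072, reached near an expected z of 2.48.

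**7. Sensitivity to the covariance (correlation 0.5, 20% attrition).** A random slope adding variance 0.2 at the last visit gives 0.637 and 0.567. AR(1) with adjacent-visit correlation 0.5 gives 0.434 and 0.364. Absolute power moves a good deal; the loss from 0.0167 to 0.0100 stays at 0.06 to 0.07.

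**8. Holm instead of Bonferroni.** 400,000 simulated sets with expected z 3.05 on every outcome and inter-outcome correlation 0 to 0.7 (assumed). Power per outcome is 0.81 to 0.83 with three tests and 0.77 to 0.80 with five, against Bonferroni's 0.75 and 0.68. If only one outcome has an effect, Holm gains almost nothing (about 0.75 and 0.68).

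These are slope tests, not the saturated treatment-by-time model of section 9.11.2. They illustrate cost and do not check the stated 80%.

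**The case against.** The best case against the point is that the document already implies three outcomes. The secondary aim names three constructs, and section 9.11.2 names their three instruments. Section 9.8.1 places those instruments under Secondary Outcomes, calls guilt cognitions a partial mediator, and describes the Brief COPE under the heading for exploratory outcomes. On this evidence the Hypothesis 2 sentence in section 8 is the likely outlier. This stands, and it makes the problem smaller. It does not remove it: section 8 still states five, nothing says which section governs, and mediator status alone cannot exclude a variable, because distress is both a Hypothesis 3 mediator and a Hypothesis 2 outcome.

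A second objection also stands in part. A reader might infer that, under the shorter list, effects on guilt cognitions and avoidant coping go untested. They do not. The second mediation condition in Hypothesis 3 requires a significant relationship between treatment and each proposed mediator, and Hypothesis 3 has its own within-hypothesis correction. What is open is the family and the confirmatory label.

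Two further inferences go beyond the text. One is that the level must be either 0.0100 or 0.0167; that holds only with one score per construct, which the plan does not settle. The other is that the conditional .01 level confirms five tests because it equals 0.05/5; the plan makes no such link.

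**Conclusion.** The point holds as an inconsistency in a secondary confirmatory family. The two lists contradict each other, and the plan's own correction rule makes the significance level depend on which is followed: 0.0100 or 0.0167 with one score per construct, lower otherwise. Three is the better-supported reading.

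The numerical effect on a single outcome is modest: at most about a 7% chance that the two levels disagree. The more important exposure is claiming all five outcomes while dividing by three, which raises the family-wise bound to 0.083. The levels and that bound are plain arithmetic. The power figures rest on the assumed covariance, visit times and dropout pattern.

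A reader might infer that the primary result is at risk. The documents do not support that: Hypothesis 1 concerns guilt severity alone, and the Hypothesis 2 list does not enter its correction.

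**What to change.** Before outcome data are seen by arm:

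1. Make the Hypothesis 2 list identical in sections 8 and 9.11.2 and state the divisor. Three is the natural choice, with guilt cognitions and avoidant coping under Hypothesis 3 only and no Hypothesis 2 claim on them. Five is acceptable.
2. Name one score per outcome: the distress measure (BSI-18 or CGI-S), the ISS score and the WHO-QOL-BREF score. Otherwise count every extra score as a test. If five is chosen, also define the Brief COPE items or subscales that make up avoidant coping.
3. Say whether the conditional .01 level applies to Hypothesis 2 and, if so, how it combines with the correction.

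As a separate improvement, use Holm at family-wise 0.05 instead of Bonferroni. It is never less powerful and needs no further assumption. It would also help to state the alpha behind the 80% power for Hypothesis 2.

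If the lists are reconciled only after data have been seen by arm, keep Bonferroni, show each Hypothesis 2 p-value against both levels, and disclose the timing.

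**Cost.** Wording only; no new data. Choosing three gives up two Hypothesis 2 claims. Choosing five costs about 0.06 to 0.07 in power per outcome under Bonferroni in the settings with correlation 0.5 or lower, and about 0.03 to 0.04 under Holm if all outcomes have the 0.5 SD effect (correlation 0.5, 20% attrition).

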Within VASDHS, we assessed feasibility of recruitment for the proposed study in regard to the inclusion criteria of having guilt related to trauma and having served in OEF/OIF/OND, neither of which are required in our current studies. Specifically, we examined what percent of participants enrolled in [name] current studies during the past year would meet the criteria regarding trauma related guilt using the Trauma Related Guilt Inventory (TRGI) and having served in OEF/OIF/OND. 27% (n = 84) of Veterans initiating outpatient PTSD treatment and 36% (n = 13) of PTSD/AUD Veterans enrolling in [name] current RCT met the OEF/OIF/OND and TRGI guilt criteria described in section 9.4 under Inclusion Criteria. We will have 28 months of active recruitment, and thus need to recruit 2-3 Veterans per month per site to reach our target of 75 at the San Diego site. Given recruitment rates in our current projects (4-5 per month), the high rates of guilt endorsed by our current OEF/OIF/OND participants, and the fact that neither AUD nor PTSD diagnosis is required for the proposed study, **our recruitment target is highly feasible.**

The Providence VA Medical Center (PVAMC) is the other site for the proposed research. The PVAMC is a 120 bed general medical facility that provides acute inpatient and outpatient care to the Veteran population throughout Rhode Island and Southeastern Massachusetts. During Fiscal Year 2014, over 2200 OEF/OIF/OND Veterans sought mental health treatment in the outpatient PTSD, General Mental Health, Returning Veterans, and Substance Abuse Treatment Program clinics. These numbers are more than sufficient to meet our recruitment goals of 2-3 Veterans per month for a total of 75 OEF/OIF/OND Veterans with deployment-related guilt and distress.

9.5.4. Attrition. Based on attrition rates in comparable research studies of exposure-based treatment for trauma related distress and our own preliminary work, we conservatively estimate that approximately up to 20% of participants will be lost to measurement follow-up prior to the final (6-month post-treatment) assessment [55]. Completion of TrIGR is defined *a priori* as attending 75% or more of the planned treatment sessions (see section 9.11.1. regarding the data analysis plan, including the plan for handling missing data and attrition).

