The Clinician-Administered PTSD Scale for DSM-5 [CAPS; 67] is a semi-structured interview used to assess PTSD diagnostic criteria and severity. Respondents select up to three of the most traumatic events they have experienced, and those events are used as the basis for assessing PTSD symptoms. The CAPS assesses each of the 20 items from the DSM-5 criteria B, C, D, and E and it has demonstrated high levels of internal consistency, good interrater reliability, and excellent convergent validity. The CAPS can be administered in about 60 minutes, and it has the advantages of categorical (diagnostic) or dimensional scoring of PTSD. The PTSD Checklist – 5 [PCL-5; 68] is a brief self-report instrument to measure PTSD symptom severity. It consists of 20 items, scored on a 5-point scale (0 = not at all to 5 = extremely), that correspond to the DSM-5 symptoms of PTSD. The PCL-5 is still being evaluated; however, preliminary studies report high internal consistency (alpha ranges between .95 and .97) and high correlations with the original PCL (between .88 and .97) [69].

Depression. The Patient Health Questionnaire [PHQ-9; 70] is a self-report scale listing common symptoms of depression. It is among the most widely used self-report depression measure in clinical populations, facilitating comparison between this investigation and others.

Exploratory outcomes. The Timeline Follow-back [TLFB; 71] will be employed at all assessment points to evaluate alcohol and other substance use during the 90 days preceding each interview. The Quantity-Frequency Index[72] and maximal consumption will be calculated for alcohol use. Drug use indices will be similarly derived for opiates, marijuana, and other drugs. The TLFB will be used at each follow-up to establish: percentage days heavy drinking, percent days abstinent, length of initial

abstinence, length of use episodes, severity of relapse and current alcohol/drug use pattern. A self-report Substance Use Inventory [SUI; 73] will be administered bi-weekly at treatment sessions. The inventory asked patients on which of the preceding seven days they had used alcohol or any of seven major types of drugs. Participants will be administered the AUD and SUD sections of the SCID for DSM-5 at baseline.

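### Section 9.11.2 names PTSD symptoms as the mediated outcome for Veterans with a depressive disorder, where Exploratory Objective 2 names depression symptoms

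*Combined protocol and SAP*

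**What the plan says.** Section 8 lists two exploratory objectives. Objective 2 concerns mediation by reductions in guilt, shame and avoidant coping. It gives each diagnostic subgroup its own outcome: PTSD symptoms for Veterans with a PTSD diagnosis, "and/or depression symptoms among" Veterans with a depressive disorder.

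The Exploratory Analyses paragraph in section 9.11.2 is the only analysis text for this objective. It says that these reductions "will partially mediate the treatment effect on PTSD symptoms among Veterans with a PTSD diagnosis and among Veterans with a depressive disorder". It introduces the question as "The second and third objectives" and sends the reader to the mediation method of Hypothesis 3.

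The same paragraph mentions depression in one other place. For the first exploratory objective, it asks whether TrIGR compared with SCT "is associated with greater decreases in PTSD and depression symptom severity".

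Section 9.8.1 supplies the depression measure: "The Patient Health Questionnaire [PHQ-9; 70] is a self-report scale listing common symptoms of depression". Section 9.8.2 lists SCID modules at baseline that identify depressive disorders.

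**The concern.** The objective and the analysis text disagree about the dependent variable in one of the two subgroups. In 9.11.2 the phrase naming PTSD symptoms governs both groups, and depression symptoms do not appear in that sentence. An analyst who works from 9.11.2 alone has a complete instruction for a model that section 8 does not request, and no instruction for the one that it does.

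The choice of outcome matters under the specified method. Three of the four conditions taken over from Hypothesis 3 involve the dependent variable: the treatment effect on it, the relation of mediator to it, and the fall in the treatment effect after adjustment for the mediator. If the outcome changes, the answer to whether mediation is supported can change with it. Two inconsistent statements also leave room to choose the outcome after the data have been seen.

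**Working it through.** The documents give no sample size, power or effect size for this analysis, so there is nothing to calculate. The check is a comparison of the two texts.

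| Element | Section 8, Objective 2 | Section 9.11.2, Exploratory Analyses | Agree? |
|---|---|---|---|
| Mediators | guilt, shame, avoidant coping | guilt, shame, avoidant coping | yes |
| Subgroups | PTSD diagnosis; depressive disorder | PTSD diagnosis; depressive disorder | yes |
| Outcome, PTSD subgroup | PTSD symptoms | PTSD symptoms | yes |
| Outcome, depressive-disorder subgroup | depression symptoms | PTSD symptoms | **no** |
| Exploratory objectives | two | refers to a second and a third | **no** |

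1. *Is either text superseded?* No. Both are current text of the same combined document, and neither comes from a log of changes.

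2. *Does another part of the plan repair the mismatch?* No. The only other use of depression in the exploratory analyses is as a direct treatment effect under the first objective. Hypothesis 3 has guilt severity as its outcome, so its method brings no depression outcome with it.

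3. *Could an instrument name settle it?* No. Hypotheses 1 to 3 name their scales in parentheses in 9.11.2, but this paragraph names none, so the PHQ-9 cannot be recovered from a label.

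4. *Does the objective count point to a cause?* It suggests one. If Objective 2 was split by outcome when it was restated, there would be a second and a third objective, with depression symptoms as the outcome of the third. That fits the loss of a few words better than a deliberate change of endpoint.

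5. *Could the two texts coincide in practice?* Not by design. Section 9.5.3 relies on "the fact that neither AUD nor PTSD diagnosis is required for the proposed study", so the depressive-disorder subgroup can include Veterans without PTSD. Even where the diagnoses overlap, PTSD severity and depression severity are different outcomes.

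**The case against.** The strongest reply is that this is a slip that nobody would act on. Section 8 states the pairing plainly, the mediators and subgroups match, and the stray third objective suggests a dropped phrase. An analyst who reads both sections would probably recover the intention. This much stands: the documents support saying that the wrong outcome *could* be used, not that it *would* be. A reader might infer that the sponsor deliberately chose PTSD symptoms for the depressive-disorder group, and nothing in the documents supports that. The slip still needs correcting, because 9.11.2 is the operative analysis text and its sentence can be carried out as written.

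A second reply is that the objective is worded with and/or, so it does not firmly commit the trial to both models. That is fair. The wording may allow the depression model to be left out, but on no reading does it put PTSD symptoms in its place as the outcome in the depressive-disorder group.

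A third reply is that the analysis is exploratory. That is correct, and it limits the weight of the point.

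Two stronger claims are tempting and should not be made. One is that an effect on PTSD symptoms would be diluted in depressed Veterans without PTSD because their scores have less room to fall. The documents give neither the share of such Veterans nor any baseline scores. Section 9.4 requires high guilt and marked distress at entry, and section 9.5.3 expects heavy recruitment from the San Diego PTSD clinic, so that share may be small. The other is that the clinician-rated CAPS must rank above the self-report PCL-5 as the PTSD endpoint. Section 9.8.1 describes both without ranking them, and the contradiction is the same whichever is used.

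**Conclusion.** The contradiction is real and in current text: sections 8 and 9.11.2 name different mediated outcomes for Veterans with a depressive disorder, and the objective counts do not match. If 9.11.2 is followed literally, one of the two subgroup mediation models is fitted to an outcome that no objective requests, and the question of mediation on depression is not answered.

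The size is limited. The primary outcome, Hypotheses 1 to 3 and the sample size do not depend on this sentence. A reader might infer that depression drops out of the analysis altogether. It does not, because depression severity is still compared directly between arms under the first exploratory objective. Only the mediation question is at risk.

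The existence of the mismatch rests on no assumption. Its consequence rests on one: that the analyst follows 9.11.2 without reconciling it with section 8. The view that a phrase was dropped is an inference from the numbering and the otherwise matching text, and the documents do not state it. The point deserves correction before analysis, as a wording repair to an exploratory objective.

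**What to change.** In the Exploratory Analyses paragraph of section 9.11.2, state the mediated outcome separately for each subgroup:

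- Veterans with a PTSD diagnosis: PTSD symptoms.
- Veterans with a depressive disorder on the baseline SCID: depression symptoms, measured by the PHQ-9, which is the depression measure listed in 9.8.1.

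Change the reference to a second and third objective so that the count matches the two in section 8. When both sections are open, it is worth saying whether both models will be run, since the and/or in Objective 2 leaves that unclear.

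The cost is about one sentence of text. The PHQ-9 and the SCID depressive-disorder modules are already in the plan, so no additional data collection, sample size or change of method is involved.
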